4.2 Scientific Rationale for Study Design

This study is designed as an observer-blind study. Participants will receive a single dose of either mRNA-1010 vaccine or a licensed quadrivalent seasonal influenza vaccine (an active comparator) to assess noninferior immunogenicity.

In this observer-blind study, participants, clinic staff involved in participant assessment, and Sponsor personnel (or its designees) will be blinded to participant vaccine allocation. A limited number of Sponsor and/or contract research organization (CRO) personnel will be unblinded to conduct safety data analyses for the DSMB safety data reviews (as described in the DSMB charter) and perform the primary analysis. Unblinded study personnel, who will not participate in any other aspect of the study, will perform investigational product (IP) accountability, dose preparation, and IP administration.

The NP swab specimen(s) for assessment of pathogens, including influenza virus and SARS-CoV-2, will be collected any time from Day 1 through Day 361 (Month 12)/EoS if the participants have protocol-defined ILI or symptoms suggestive of COVID-19 or other upper or lower respiratory infection at the investigator's discretion (see [Section 8.11.5](#)). If participants experience these signs or symptoms, they will be instructed to contact the clinic to have an NP swab collected for testing. Nasopharyngeal swabs may be collected as part of a home visit in lieu of a clinic visit. In the event that NP swabs during ILI cannot be collected by the study staff, any available influenza and/or SARS-CoV-2 testing results performed by a certified laboratory outside of the study should be captured in the eCRF.

4.3 Justification for Dose, Control Product, and Choice of Study Population

The Sponsor's Phase 1/2 mRNA-1010-P101 study is currently ongoing to provide initial first-in-human safety and immunogenicity data on 3 dose levels of mRNA-1010 encoding strains (50, 100, or 200 µg total mRNA) recommended by the WHO for the 2021 SH. An amendment to mRNA-1010-P101 includes a Phase 2 NH portion to the study to increase the size of the safety database for the 50 µg and 100 µg dose levels and to test an additional 25 µg dose level of mRNA-1010 as well as a licensed seasonal influenza vaccine as an active comparator (Fluarix Tetra). Fluarix Tetra was selected as an active comparator because it is licensed for the prevention of influenza disease caused by vaccine-matched strains in the target population (≥ 18 years old) in SH countries. A Phase 2 Extension portion is ongoing to study additional dose levels of mRNA-1010 (6.25 µg and 12.5 µg) as well as 25 µg of mRNA-1010 and an active comparator.

No significant safety concerns have been observed in the ongoing Phase 1/2 mRNA-1010-P101 study upon review of safety data up to 29 days by the DSMB. The 50-µg dose of mRNA-1010 showed a preferable reactogenicity profile. Vaccination with mRNA-1010 elicited HAI

antibodies in both younger and older adults against all strains at all dose levels. HAI titers elicited at the 50 µg dose level were comparable with the titers elicited at higher dose levels.

The interim analysis from the Phase 2 NH part of mRNA-1010-P101 through Day 29 demonstrated no significant safety concerns at any dose level (25, 50, or 100 µg) (further details are provided in the current IB).

4.4 End of Study Definition

A participant is considered to have completed the study if they complete the final visit on Day 361 (Month 12) as shown in the SoE ([Table 1](#)).

The EoS is defined as completion of the last visit of the last participant in the study or last scheduled procedure as shown in the SoE ([Table 1](#)) for the last participant in the study.

5. STUDY POPULATION

Approximately 6000 participants will be enrolled in a 1:1 ratio to receive either a single dose of mRNA-1010 or a single dose of a licensed seasonal influenza vaccine (Fluarix Tetra) as an active comparator (approximately 3000 participants in each vaccination group).

Prospective approval of protocol deviations to recruitment and enrollment criteria, also known as protocol waivers or exemptions, is not permitted.

5.1 Inclusion Criteria

Participants are eligible to be included in the study only if all the following criteria apply:

1. Individual is at least 18 years of age at the time of consent (Screening Visit).
2. Investigator has assessed that the participant understands and is willing and physically able to comply with protocol mandated follow-up, including all procedures.
3. Participant has provided written informed consent for participation in this study, including all evaluations and procedures as specified by this protocol.
4. Female participants of nonchildbearing potential may be enrolled in the study. Nonchildbearing potential is defined as post-menopausal or permanently sterilized. Follicle-stimulating hormone (FSH) may be measured at the discretion of the investigator to confirm postmenopausal status (see additional information in [Section 11.2](#)).
5. Female participants of childbearing potential may be enrolled in the study if the participant fulfills all the following criteria:
 - Has a negative pregnancy test at the Screening Visit and on the day of vaccination prior to vaccine dose being administered on Day 1.
 - Has practiced adequate contraception or has abstained from all activities that could result in pregnancy for at least 28 days prior to the first dose (Day 1). Adequate female contraception is defined as consistent and correct use of a local health authority-approved contraceptive method in accordance with the product label.
 - Has agreed to continue adequate contraception through 90 days following vaccine administration.

5.2 Exclusion Criteria

Participants are excluded from the study if any of the following criteria apply:

1. Participant has had close contact to someone with SARS-CoV-2 infection or COVID-19 as defined by the US CDC or has had a positive SARS-CoV-2 test in the past 10 days prior to the Screening Visit.

2. Participant is acutely ill or febrile (temperature $\geq 38.0^{\circ}\text{C}$ [100.4°F]) 72 hours prior to or at the Screening Visit or Day 1. Participants meeting this criterion may be rescheduled within the 28-day screening window and will retain their initially assigned participant number.
3. Participant has a history of a diagnosis or condition that, in the judgment of the investigator, is clinically unstable or may affect participant safety, assessment of safety endpoints, assessment of immune response, or adherence to study procedures. Clinically unstable is defined as a diagnosis or condition requiring significant changes in management or medication within the 60 days prior to the Screening Visit and includes ongoing workup of an undiagnosed illness that could lead to a new diagnosis or condition.
4. Reported history of congenital or acquired immunodeficiency, immunocompromising/immunosuppressive condition, asplenia, or recurrent severe infections. The following conditions are permitted at the discretion of the Investigator:
 - a) Participants who are HIV positive and on antiretroviral therapy with cluster of differentiation 4 count ≥ 350 cells/ mm^3 and HIV RNA ≤ 500 copies/mL within the past 12 months.
 - b) Participants with immune-mediated diseases which are stable (eg, Hashimoto's thyroiditis and type 1 diabetes) or conditions such as asthma, psoriasis, vitiligo, gout, alopecia areata, or autoimmune ovarian failure which do not require systemic immunosuppressants per Exclusion Criterion 9.
5. Dermatologic conditions that could affect local solicited adverse reaction (AR) assessments (eg, tattoos, psoriasis patches affecting skin over the deltoid areas).
6. Reported history of anaphylaxis or severe hypersensitivity reaction after receipt of any mRNA or influenza vaccines or any components of the mRNA or influenza vaccines, including egg protein.
7. Reported history of coagulopathy or bleeding disorder that is considered a contraindication to IM injection or phlebotomy.
8. Any medical, psychiatric, or occupational condition, including reported history of substance abuse, that, in the opinion of the investigator, may pose additional risk due to participation in the study or that could interfere with the interpretation of study results.
9. Participant has received systemic immunosuppressants or immune-modifying drugs for > 14 days in total within 180 days prior to the Screening Visit (for corticosteroids, ≥ 10 mg/day of prednisone or equivalent) or is anticipating the need for systemic immunosuppressive treatment at any time during participation in the study. Inhaled, nasal, and topical steroids are allowed.

10. Participant has received any vaccine authorized or approved by local health agency \leq 28 days prior to study injection (Day 1) or plans to receive a vaccine authorized or approved by local health agency within 28 days before or after the study injection.
11. Participant is not aware whether they have received an influenza vaccine in the past 12 months.
12. Participant has received a seasonal influenza vaccine or any other investigational influenza vaccine within 180 days prior to Day 1.
13. Participant has tested positive for influenza by local health authority-approved testing methods within 180 days prior to the Screening Visit.
14. Participant has a history of myocarditis, pericarditis, or myopericarditis within 60 days prior to the Screening Visit. Participants who have not returned to baseline after their convalescent period will also be excluded.
15. Participant has received systemic immunoglobulins or blood products within 90 days prior to the Screening Visit or plans to receive systemic immunoglobulins or blood products during the study. In addition, participants who have received long-acting biological therapies that affect immune responses (eg, infliximab) within 90 days prior to the Screening Visit, or plan to receive them, are also excluded.
16. Participant has donated \geq 450 mL of blood products within 28 days prior to the Screening Visit or plans to donate blood products during the study.
17. Participant has participated in an interventional clinical study within 28 days prior to the Screening Visit based on the medical history interview or plans to do so while participating in this study.
18. Participant is an immediate family member or household member of study personnel, clinic staff, or Sponsor personnel.

5.3 Lifestyle Restrictions

Participants must not eat or drink anything hot or cold within 10 minutes before oral temperature is taken. Participants in the study should defer vaccination with licensed seasonal influenza vaccine until after completion of their Day 29 visit, and ideally until Day 181 Visit, if seasonal influenza vaccine is available, and they have discussed with the investigators and have chosen to receive it.

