4. STUDY DESIGN

4.1 General Design

This is a Phase 3, randomized, stratified, observer -blind, active -controlled study to evaluate the immunogenicity and safety of mRNA-1010 vaccine in preventing seasonal influenza in adults aged 18 years and older.

The mRNA-1010 vaccine to be tested includes mRNAs encoding for the surface HAs of the influenza strains recommended by the WHO for 2022 SH cell- or recombinant-based vaccines:

- A/Wisconsin/588/2019 (A/H1N1)like virus;
- A/Darwin/6/2021 (A/H3N2)like virus;
- B/Michigan/01/2021 (B/Victoria lineage)like virus; and
- B/Phuket/3073/2013 (B/Yamagata lineage)like virus.

Study vaccine administration is planned prior to or during the typical SH influenza vaccination campaign period. Medically stable adults, aged 18 years and older, will be screened and enrolled. A complete list of inclusion and exclusion criteria is provided in [Section 5](#).

The Sponsor's Phase 1/2 mRNA-1010-P101 study is currently ongoing to provide initial first-in-human safety and immunogenicity data on 3 dose levels of mRNA-1010 encoding strains (50, 100, or 200 µg total mRNA) recommended by the WHO for the 2021 SH. An amendment to mRNA-1010-P101 includes a Phase 2 NH portion to the study to increase the size of the safety database for the 50 µg and 100 µg dose levels and to test an additional 25 µg dose level of mRNA-1010 as well as a licensed seasonal influenza vaccine as an active comparator. mRNA-1010 encoding strains for the 2021 to 2022 NH will be used in the Phase 2 NH portion. A Phase 2 Extension portion is assessing additional dose levels of 6.25 µg and 12.5 µg mRNA-1010 as well as 25 µg mRNA-1010 and an active comparator. The interim analysis of safety data through Day 29 of 180 healthy adults in the Phase 1/2 portion of mRNA-1010-P101 showed preferable reactogenicity profile for the 50 µg dose of mRNA-1010. The Phase 2 NH interim analysis of safety data through Day 29 demonstrated no significant safety concerns of the dose levels tested (25, 50, and 100 µg).

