6.5.1 Recording of Concomitant Medications, Concomitant Vaccinations, and Concomitant Procedures

The following concomitant medication(s) and vaccine(s) must be recorded in the eCRF:

- Any vaccine (authorized or investigational) administered in the prior 12 months.
- All concomitant medications and non-study vaccines taken through 28 days after the IP injection. Antipyretics and analgesics taken prophylactically (ie, taken in the absence of any symptoms in anticipation of an injection reaction) will be recorded as such.

- Any authorized or investigational COVID-19 vaccine at any time before or during the study period after the IP injection.
- Any authorized influenza vaccine at any time during the study period after the IP injection.
- All concomitant procedures/surgeries at any time during the study period after the IP injection.
- Immunosuppressants or other immune-modifying drugs administered chronically (ie, more than 14 days in total) and systemic steroids (≥ 10 mg/day prednisone or equivalent) , administered at any time during the study period after the IP injection.
- Immunoglobulins and long-acting biological therapies that affect immune responses (eg, infliximab) and/or any blood products administered during the study period.
- Any concomitant medications relevant to or for the treatment of an SAE, AESI, or medically attended AE (MAAE) from Day 1 through Day 361 (Month 12)/EoS.
- The participant will be asked in the eDiary if they have taken any antipyretic or analgesic to treat or prevent fever or pain within 7 days after the IP injection, including the day of injection. Reported antipyretic or analgesic medications should be recorded in the source document by the clinic staff during the clinic visits after vaccination or via other participant interactions (eg, telephone calls).

Concomitant medications (including vaccinations) will be coded using the WHO Drug Global.

If a participant takes a prohibited drug therapy, the investigator and the CRO's medical monitor will make a joint decision about continuing or withholding the study vaccination of the participant based on the time the medication was administered, the drug's pharmacology and pharmacokinetics, and whether use of the medication will compromise the participant's safety or interpretation of the data. It is the investigator's responsibility to ensure that details regarding the concomitant medications are adequately recorded in the eCRF.

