6.5.2 Concomitant Medications and Vaccines That May Lead to the Elimination of a Participant From Per-protocol Analyses

The use of the following concomitant medications and/or vaccines will not require withdrawal of the participant from the study but may determine a participant's evaluability in the per-protocol (PP) analysis (analysis sets are described in [Section 9.4](#)):

- Any investigational or nonregistered product (drug or vaccine) other than the IP used during the study period.
- Immunosuppressants or other immune-modifying drugs administered chronically (ie, more than 14 days in total) during the study period. For corticosteroids, this will mean that prednisone ≥ 10 mg/day or the equivalent is not permitted. Inhaled, nasal, and topical steroids are allowed.

- An authorized or licensed vaccine administered within 28 days after the study vaccination.
- Immunoglobulins and long-acting biological therapies that affect immune responses (eg, infliximab) and/or any blood products administered during the study period.

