The mITT Set consists of all participants in the FAS who provide any follow-up for ILI beginning at least 14 days following administration of study intervention. Participants will be analyzed according to the group to which they are randomized to.

The mITT Set is the primary population for the analysis of efficacy data.

PP Set for Efficacy

The PP Set for Efficacy consists of all participants in the mITT Set who have no significant protocol deviations that impact key or critical efficacy data. Participants will be analyzed according to the group they are randomized to.

Immunogenicity Set

The Immunogenicity Set consists of all participants in the FAS who have baseline and Day 29 antibody assessment via HAI assay. Participants will be analyzed according to the group to which they were randomized.

PP Immunogenicity Set

The PP Immunogenicity Set includes all participants in the Immunogenicity Set who received planned dose of IP, complied with the immunogenicity testing schedule, and had no significant protocol deviations that impact key or critical data. Participants with RT-PCR-confirmed influenza between Days 1 to 29 will be removed from the PP Immunogenicity Set.

The PP Immunogenicity Set is the primary population for the analysis of immunogenicity data in the study unless specified otherwise. Participants will be analyzed according to the group to which they are randomized to.

For PP Set for Efficacy and PP Immunogenicity Set, the following major dosing error ranges for planned mRNA-1010 and active comparator will be used to determine participant exclusion from the analysis populations:

Table 3 Exclusion Criteria for Dosing Errors

Actual Vaccine Received	Planned (mRNA-1010 50 µg)
mRNA-1010 ≤ 37.5 µg	Yes ¹
mRNA-1010 >37.5 µg – 62.5 µg	No
mRNA-1010 > 62.5 µg	Yes
Active Comparator ²	Yes

1. Yes means major dosing error
2. Active comparator is Fluarix Tetra (pre-filled syringe)

Table 4 Major Dosing Errors for Active Comparator

Actual Vaccine Received	Planned (Active Comparator²)
Fluarix Tetra ≤ 45 µg	Yes ¹
Fluarix Tetra > 45 µg – 60 µg	No
Any mRNA-1010	Yes

1. Yes means major dosing error
2. Active comparator is Fluarix Tetra (pre-filled syringe)

Solicited Safety Set

The Solicited Safety Set consists of all randomized participants who received any study vaccination and contributed any solicited AR data, i.e., had at least one post-baseline solicited safety assessment.

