6.3.3 Analysis of Exploratory Immunogenicity Endpoints

- Analyses of GMT and GMFR of nAbs by MN assays against vaccine-matched or vaccine-mismatched strains on Day 29, compared with Day 1 (baseline)
- Analyses of GMT and GMFR of anti-HA antibodies as measured by HAI against vaccine-mismatched strains on Day 29
- Analyses of GMT and GMFR of anti-HA antibodies as measured by HAI against vaccine-matched or vaccine-mismatched strains, on Day 181 and Day 361/EoS compared with Day 1 (baseline)

Descriptive statistics (n, median, min, max) will be provided for the following endpoints with corresponding 95% CI at each time point. The 95% CIs will be calculated based on the t-distribution of the log-transformed values then back transformed to the original scale for presentation. In addition, the GMT and GMFR with corresponding 95% CI will be plotted at each time point respectively.

The number and percentage of participants with an HAI titer $\geq 1:40$ post-injection due to vaccination at Day 181 and Day 361 will be provided with 2-sided 95% CI using the Clopper-Pearson method.

To further characterize the immune response to mRNA-1010 and active comparator, frequency, specificities, or other endpoints may be determined for further characterization of immune responses. A reverse cumulative distribution function plot of anti-HA antibody levels for HAI assay by visit will be provided.

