9.8 Estimands and Estimand Specifications

Table 11: Intercurrent Events

Label	Intercurrent Event Type
IcEv1 (early discontinuation or unrelated death)	Early discontinuation from study or unrelated death prior to Day 29, the first post-treatment immunogenicity result available.
IcEv2 (alternative influenza vaccine)	Use of alternative Influenza vaccine prior to Day 29.
IcEv3 (COVID-19 vaccine)	Use of COVID-19 vaccine prior to Day 29.
IcEv4 (prohibited medications)	Use of prohibited medications deemed to impact on immunogenicity prior to Day 29.
IcEv5 (early infection)	Infection starting up to 29 days after IP injection.
IcEv6 (wrong vaccination)	Receiving wrong vaccination.

Abbreviation: IcEv: intercurrent event.

Table 12: Summary of Primary Immunogenicity Estimands with Rationale for Strategies to Address Intercurrent Events

Objective: To evaluate the humoral immunogenicity of mRNA-1010 relative to that of the active comparator against vaccine-matched influenza A and B strains at Day 29 based on HAI assays		
Estimand Label	Primary Immune Estimand 1a (on the PP Immunogenicity Set)	Supportive Immune Estimand 1b (on the Immunogenicity Set)
Estimand Description	Immune response to influenza measured as GMT ratio of anti-HA level as measured by HAI assay on Day 29 in adults aged 18 years or older who receive IP administration and complied with immunogenicity blood sampling to have a baseline and at least 1 post-injection antibody assessment without significant protocol deviations impacting immune response and RT-PCR-confirmed influenza between Days 1 to 29.	Immune response to seasonal influenza measured as GMT ratio of anti-HA level as measured by HAI assay on Day 29 in adults aged 18 years or older who receive IP administration irrespective of any significant protocol deviations impacting immune response and complied with immunogenicity blood sampling to have a baseline and at least 1 post-injection antibody assessment as measured by HAI assay.

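### Day 181 and Day 361 titer summaries have no rule for samples taken after a permitted non-study influenza vaccine or a later influenza infection, so persistence may be overstated, mainly at Day 361 (minor)

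*Protocol*

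**What the plan says.** Protocol 5.3 asks participants to defer licensed seasonal influenza vaccine until the Day 29 visit is done, and "ideally until Day 181 Visit, if seasonal influenza vaccine is available". Between Day 181 and Day 361 there is no restriction. On timing, Protocol 4.1 states: "Study vaccine administration is planned prior to or during the typical SH influenza vaccination campaign period". The synopsis expects the first enrolment in June 2022 and the last completion in August 2023.

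The rules that handle these exposures stop early:

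- SAP Section 5, PP Immunogenicity Set: "Participants with RT-PCR-confirmed influenza between Days 1 to 29 will be removed from the PP Immunogenicity Set".
- Protocol 6.5.2, products that may affect per-protocol evaluability: "An authorized or licensed vaccine administered within 28 days after the study vaccination".
- SAP 9.8, Table 11, intercurrent events: "Use of alternative Influenza vaccine prior to Day 29" and "Infection starting up to 29 days after IP injection".

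SAP 6.3.3 plans GMT and GMFR by HAI against "vaccine-matched or vaccine-mismatched strains, on Day 181 and Day 361/EoS compared with Day 1 (baseline"), and the proportion with a titer of at least 1:40 at both late visits, which it describes as attributable to vaccination. Seroconversion at Days 181 and 361 is listed among the exploratory endpoints in SAP 3.2. By default (SAP 6.3) these summaries use the PP Immunogenicity Set, and late samples are analysed only in a subset of the first 1000 randomised participants.

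Protocol 6.5.1 does require the relevant vaccine data to be recorded: "Any authorized influenza vaccine at any time during the study period after the IP injection".

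**The concern.** The late titers are there to show how long the response to each study vaccine lasts. A sample drawn after a second influenza vaccine, or after influenza, may measure the response to that event instead. The protocol recognises the problem at entry: exclusion criteria 12 and 13 bar an influenza vaccine in the 180 days before Day 1 and a positive influenza test in the 180 days before screening. No comparable rule protects the late samples.

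A reader of the tables could not judge the extent of the problem either. The planned table of non-study influenza vaccine in SAP 6.2.4 stops at 28 days, so later use appears only in a listing. At stake is whether the trial's only durability data can be attributed to the study vaccines.

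**Working it through.** **Is there a rule that covers these samples?** The windows, side by side:

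| Provision | Exposure | Window |
|---|---|---|
| SAP 5, PP Immunogenicity Set | RT-PCR-confirmed influenza | Days 1 to 29 |
| Protocol 6.5.2 | Licensed vaccine | 28 days after injection |
| Protocol 6.5.2 | Investigational or unregistered product | Whole study |
| SAP 9.8, alternative influenza vaccine | Influenza vaccine | Before Day 29 |
| SAP 9.8, early infection | Infection | Up to 29 days |
| SAP 9.3, Table 7 | Late samples | Assigned by study day only |

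Only investigational or unregistered products are covered beyond Day 29. The estimands in SAP 9.8 concern Day 29, and none is defined for Days 181 or 361.

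**Can exposure fall before the late samples?** Day 361 is 360 days after Day 1, close to the same calendar date a year later. A participant injected before or during one campaign therefore passes through the rest of that campaign and whatever part of the next precedes the anniversary. Influenza infection is also expected: Day 14 to Day 181 or the end of the season is the trial's own efficacy window.

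**How large could the effect be?** The documents give no figure for late samples to reproduce, and neither of the two inputs needed: the share of late samples affected, p, and the fold rise in those samples, f. Both are assumed here. On the log scale the mean shifts by p × ln f, so

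shown GMT = true GMT × f^p.

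GMFR is inflated by the same factor, because the baseline is unaffected.

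| p | f = 1.5 | f = 2 | f = 4 |
|---|---|---|---|
| 2% | 1.01 | 1.01 | 1.03 |
| 5% | 1.02 | 1.04 | 1.07 |
| 10% | 1.04 | 1.07 | 1.15 |
| 30% | 1.13 | 1.23 | 1.52 |

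For scale, take the SD of 1.5 on the natural-log scale from Protocol 9.3 (an assumption made for Day 29) and at most 1000/2 = 500 per arm. The 95% CI factor for one GMT is exp(1.96 × 1.5/√500) = 1.14. The possible bias is inside that at 5% affected, and about equal to it or larger at 30%.

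For titers of at least 1:40, assume a true 50% and that 95% of affected samples reach 1:40. The shown proportion is 0.50 × (1 − p) + 0.95 × p: about 52% at p = 5%, 54.5% at 10% and 63.5% at 30%.

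**What happens to the contrast between arms?** Let R be the true ratio of late GMTs.

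- Same p and same f in both arms: R × f^p / f^p = R, so nothing changes.
- Affected samples reach one common level in both arms, same p: R^(1−p). R = 1.20 at p = 30% shows as 1.14.
- Same f, different p: R × f^(pT − pC), where pT and pC are the shares in the mRNA-1010 and comparator arms. With f = 4 and R = 1.20, 3% against 5% gives 1.17, and 5% against 3% gives 1.23.

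The direction is therefore not determined.

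**The case against.** Several points on the other side are sound.

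- **Status.** The protocol presents these endpoints as exploratory and optional. They are descriptive, outside multiplicity control (SAP 6.5) and limited to a subset. This stands, and it sets the severity.
- **Day 181 is partly protected.** Deferral to that visit is encouraged. This stands; the weight of the point is at Day 361.
- **The size is assumed.** Uptake and boost are not in the documents. Strain recommendations are also revisited each season (Protocol 2.1), so the boost against the 2022 strains is uncertain. This stands, so overstatement is conditional.
- **Summarising all samples is a legitimate treatment-policy choice.** The SAP uses that strategy in its supportive Day 29 estimands. But no strategy is stated for the late visits, and describing a late 1:40 proportion as attributable to vaccination does not fit it.
- **Deviation rules are still open.** SAP 6.2.5 leaves significant-deviation rules to be finalised before database lock. A vaccine that Protocol 5.3 permits is not plainly a deviation, so this does not close the gap.
- **Removing infected participants can itself bias.** Infection after randomisation may depend on vaccine efficacy and on titer. This stands, and it limits what the main analysis should exclude.

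A reader might infer that later vaccination pulls the arms together. The documents do not support that: it requires affected samples to reach a common level in both arms, and SAP 6.3.3 plans no between-arm ratio or test at the late visits. Nor are the late summaries run on everyone with a sample; they use PP-set participants within the late-sample subset.

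**Conclusion.** The gap is real. Followed as written, the plan counts titers measured after a permitted influenza vaccine, or after influenza beyond Day 29, as persistence of the study vaccine response. If such exposures occur and raise the measured titer, late GMT, GMFR and titers of at least 1:40 are biased upward, mainly at Day 361; late seroconversion is exposed in the same way. For an assumed 1.5- to 4-fold boost the GMT inflation is about 1.02- to 1.07-fold at 5% affected and 1.13- to 1.52-fold at 30%. No single figure can be derived from the documents, and the effect on the comparison of arms could go either way. No primary or alpha-controlled result is affected. Severity: minor.

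**What to change.** In SAP 6.3.3, make the main Day 181 and Day 361 summaries (GMT, GMFR, seroconversion and titers of at least 1:40) exclude samples collected after receipt of a non-study influenza vaccine, counted from that date. Samples taken before that date stay in. Keep the all-samples summary as supportive.

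Add a sensitivity summary that also excludes samples after RT-PCR-confirmed influenza. State its limits: it conditions on a post-randomisation outcome that vaccine efficacy may affect, and symptom-triggered swabbing misses asymptomatic infection.

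Report the number of affected samples by arm and visit, and extend the non-study influenza vaccine table in SAP 6.2.4 from 28 days to Day 361.

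The cost is SAP wording, one derivation and a longer table window. No new data are needed: Protocol 6.5.1 collects influenza vaccines throughout, and Protocol 8.9.2 provides for swabs of symptomatic illness to Day 361. The downside is a smaller late sample within an already limited subset.
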